#### **Follow up:**

All patients will be followed-up regularly at 3 and 6 months postoperatively with the IPSS, Qmax, PVR, IIEF-5Q, MSHQ-EjD Short Form, and rates of complications (including urethral stricture, incontinence, bladder neck contracture, Recatheterisation, UTI, and retrograde ejaculation).

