**Statistical analysis:**

Statistical analysis was done by SPSS v26 (IBM Inc., Chicago, IL, USA). Shapiro-Wilks test and histograms were used to evaluate the normality of the distribution of data. Quantitative parametric variables were presented as mean and standard deviation (SD) and compared between the two groups utilizing unpaired Student's T- test. Quantitative non-parametric data were presented as median and interquartile range (IQR) and were analyzed by Mann-Whitney test. Qualitative variables were presented as frequency and percentage and were analyzed utilizing the Chi-square test or Fisher's exact test when appropriate. A two tailed P value  $< 0.05$  was considered statistically significant

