## Results

In this study, 103 patients were assessed for eligibility; 8 patients did not meet the criteria and 5 patients refused to participate in the study. The remaining patients were randomly allocated into two equal groups (45 patients in each). All allocated patients were followed-up and analyzed statistically (**Figure 42**).

[figure not shown]

[figure not shown]
Figure 1: CONSORT flow chart of the enrolled patients.

[figure not shown]

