**Figure 5: IIEF-5Q of the studied groups.**

**Table 4: MSHQ-EjD score of the studied groups**

	Group 1 (n=43)	Group 2 (n=41)	P value	Mean difference (95% CI)
Preoperative (1-15)	12.42±1.23	10.98±2.16	<0.001*	1.44(0.708: 2.181)
3 months postoperative	10.26±1.42	9.63±1.77	0.284	0.632(-0.544: 1.808)
6 months postoperative	10.62±1.76	10.38±2.26	0.741	0.243(-1.232: 1.717)

\*Significantly different as P value  $\leq 0.05$ , CI: Confidence interval, MSHQ-EjD: Male sexual health questionnaire – ejaculatory dysfunction short form, TTT: Treatment

MSHQ-EjD score was significantly higher at preoperative (1-15) in group 1 than group 2 (P value <0.001) and was insignificantly different at three and six months postoperative between both groups.

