**Figure 16: Complications of the studied groups.**

**Table 10: Post-operative preserved ejaculation, semen volume and concentration of the studied groups**

[figure not shown]
		Group 1 (n=43)	Group 2 (n=41)	P value	Median, mean difference or RR (95% CI)
Preserved ejaculation	After 3 months	35 (81.4%)	8 (19.51%)	<0.001*	18.05(6.07:53.64)
	After 6 months	34 (79.07%)	8 (19.51%)	<0.001*	15.58(5.37:45.25)
Semen volume (mL)	After 3 months	2.37±0.78	2.01±0.58	0.223	0.362(-229: 0.953)
	After 6 months	2.41±0.78	2.49±0.73	0.797	-0.079(-0.165: 0.535)
Sperm concentration (million sperm/mL)	After 3 months	35 (13.75-82)	72 (62.75-89.25)	0.036*	37(8: 60)
	After 6 months	32.5 (13-72)	86. (76-106.75)	0.005*	54(20: 78)

\*Significantly different as P value ≤0.05, CI: Confidence interval, RR: Relative risk

[figure not shown]
Preserved ejaculation (after three and six months) were significantly higher in group 1 than group 2 (P value <0.001).

Semen volume (after three and six months) was insignificantly different between both groups.

[figure not shown]
Sperm concentration (after three and six months) was significantly lower in group 1 than group 2 (P value<0.05).

**Figure 17:** Preserved ejaculation of the studied groups.

**Figure 18:** Semen volume of the studied groups.

[figure not shown]
**Figure 19:** Sperm concentration of the studied groups.

[figure not shown]

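### Table 10 counts an undefined preserved ejaculation, and the mean ejaculation score of the group 1 men so counted appears to have fallen by at least 1.5 points at 3 months and 1.1 at 6 months, which the text does not report

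*Combined protocol and SAP*

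**What the plan says.** Pre-operative Evaluation and Follow up make the MSHQ-EjD short form the ejaculation questionnaire, taken before surgery and at 3 and 6 months. Follow up also plans "rates of complications (including urethral stricture, incontinence, bladder neck contracture, Recatheterisation, UTI, and retrograde ejaculation". Neither section defines preserved ejaculation, no primary endpoint is named, and no MSHQ-EjD threshold or smallest important change is given.

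The Statistical analysis section says continuous outcomes were "compared between the two groups utilizing unpaired Student's T- test". It contains no paired or change-from-baseline analysis.

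Table 10 gives preserved ejaculation as 35/43 and 34/43 in group 1 and 8/41 at both visits in group 2, with the comment "Preserved ejaculation (after three and six months) were significantly higher in group 1 than group 2 (P value <0.001". Tables 11 to 13 reuse the same outcome.

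Table 4 shows the group 1 mean MSHQ-EjD at 12.42 (SD 1.23) before surgery, 10.26 (1.42) at 3 months and 10.62 (1.76) at 6 months. Group 2 has 10.98 (2.16), 9.63 (1.77) and 10.38 (2.26). The column heads read n=43 and n=41 for every row. The comment is "MSHQ-EjD score was significantly higher at preoperative (1-15) in group 1 than group 2 (P value <0.001", followed by a statement that the arms did not differ significantly after surgery. The fall within group 1 is not mentioned.

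**The concern.** A reader told that about four men in five had preserved ejaculation may take it that ejaculation stayed as it was. Table 4 points the other way for the average man in group 1, and the two tables are never connected. If the Table 4 postoperative means come only from the men whom Table 10 counts as successes, the document holds evidence that those same men scored lower than before surgery, and neither the planned tests nor the commentary shows it.

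The study aim names ejaculation as one of three efficacy domains, and the Introduction stresses the balance between symptom relief and sexual function. How much function the technique keeps is therefore central. An undefined yes/no count cannot answer that, and a between-arm comparison of scores among successes only does not answer it either.

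**Working it through.** **1. Reproduce Table 10.** 35/43 = 81.4%, 34/43 = 79.07%, 8/41 = 19.51%. All agree.

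**2. Which men are behind Table 4?** The plan's test is Student's t, so half-width = t(0.975, n1+n2−2) × sp × √(1/n1 + 1/n2), with sp the pooled SD. I used the printed SDs and differences of the printed means (1.44, 0.63, 0.24).

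| Row | Printed | n=43/41 | Best-fitting reported n |
|---|---|---|---|
| Before surgery | "1.44(0.708: 2.181" | 0.682 to 2.198 | 45/45: 0.704 to 2.176 |
| 3 months | "0.632(-0.544: 1.808", P=0.284 | −0.065 to 1.325, P=0.075 | 35/8: −0.546 to 1.806, P=0.286 |
| 6 months | "0.243(-1.232: 1.717", P=0.741 | −0.637 to 1.117, P=0.588 | 34/8: −1.235 to 1.715, P=0.744 |

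Example at 3 months with 35/8: sp = 1.4856, standard error = 0.5822, t(41) = 2.0195, half-width = 1.176. The printed half-width is (1.808 + 0.544)/2 = 1.176. The baseline row fits the allocation, "randomly allocated into two equal groups (45 patients in each".

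**3. Supporting checks.**
- If scores are whole numbers, a 6-month mean of 10.62 is impossible with n=43 (456/43 = 10.60, 457/43 = 10.63), and 10.38 is impossible with n=41 (425/41 = 10.37, 426/41 = 10.39). Both are possible with 34 (361/34 = 10.618) and 8 (83/8 = 10.375). At 3 months this check does not discriminate.
- Other pairs, such as 21/11, also give the printed interval widths. They match no count in the document, and 10.38 is not attainable with 11 men (114/11 = 10.36, 115/11 = 10.45).
- Semen volume at 3 months in Table 10 shows the same pattern: 35/8 gives P=0.227 (printed 0.223), 43/41 gives P=0.019.

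**4. Smallest possible fall in group 1.** Among N men with mean m and SD s, the lowest mean that any n of them can have is m − s × √((N−1)/N) × √((N−n)/n). With N=45, m=12.42, s=1.23:
- 3 months, n=35: 12.42 − 1.23 × 0.9888 × 0.5345 = 12.42 − 0.65 = 11.77. Fall ≥ 11.77 − 10.26 = **1.51**.
- 6 months, n=34: 12.42 − 1.23 × 0.9888 × 0.5688 = 12.42 − 0.69 = 11.73. Fall ≥ 11.73 − 10.62 = **1.11**.

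Worst-case rounding of the inputs lowers these only to 1.50 and 1.10. If the men's baseline equalled the arm mean, the falls are 2.16 and 1.80. The upper limits are 2.81 and 2.49.

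**5. Group 2.** With n=8 of 45, the same formula moves the baseline mean by 2.16 × 0.9888 × √(37/8) = 4.59 either way. The change could run from a rise of 3.2 to a fall of 5.9 at 3 months, and from a rise of 4.0 to a fall of 5.2 at 6 months. That is uninformative.

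**6. If the column heads were right after all.** With all 43 men scored, the 35 successes could average at most 10.26 + 1.42 × √(42/43) × √(8/35) = 10.93 at 3 months, and the 34 at most 10.62 + 1.76 × √(42/43) × √(9/34) = 11.51 at 6 months. The floors for the successes shrink to 11.77 − 10.93 = 0.84 and, before rounding, 11.728 − 11.515 = 0.21.

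**The case against.** The strongest reply is that the count and the score answer different questions. The Introduction frames the problem as antegrade against retrograde or dry ejaculation, and Follow up lists retrograde ejaculation, whose natural counterpart is the Table 10 row. A man can ejaculate antegrade and still score lower. The comment under Table 10 is a between-arm statement, and nothing here disturbs it. This stands. A reader might infer that 81% and 79% overstate preserved function, but the documents do not support that: the term is undefined, no important change is specified, and a mean fall does not say how many men declined. No corrected percentage can be computed.

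A reader might also infer that the 1.5 and 1.1 point floors hold whoever was scored. They do not. They rest on an inference about n that the document does not state, and under the printed column heads they drop to 0.84 and 0.21. The fit in Table 4 is close enough to make the inference the likely one, but only the data can settle it.

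Third, group 1 started 1.44 points above group 2, so some of the fall may be regression to the mean. That also stands. As a rough gauge, against the pooled baseline of (12.42 + 10.98)/2 = 11.70 the later group 1 means are still 1.44 and 1.08 lower. That does not measure the regression effect, and with a group 2 bound this wide the fall cannot be compared between arms.

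Finally, the means are printed in Table 4, so the fall is not hidden. It is not described, and the n beside it appears wrong.

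**Conclusion.** The concern holds in a limited form. Preserved ejaculation is neither defined nor tied to the MSHQ-EjD, so 81.4% and 79.07% do not on their own establish that ejaculatory function was kept. Table 4's postoperative rows carry an n that their own intervals contradict. Among the counts the document reports, only 35/8 and 34/8 fit.

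If those are the scored men, the group 1 successes lost at least about 1.5 points on average at 3 months and 1.1 at 6 months on a scale printed as 1 to 15. This assumes that the baseline row covers all 45 men in the arm, as its interval suggests, and that the scored men are those counted as preserved. It is a statement about a mean in group 1 only. It does not isolate the effect of surgery from regression to the mean, does not extend to group 2, and gives no number of men who worsened.

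**What to change.** 1. Name the Table 10 row by what was counted, for example any antegrade ejaculation if that is what it was, and say how it was ascertained. Carry the same label into Tables 11 to 13.
2. Correct n in each row of Table 4 and state which men were scored at each visit.
3. Report the mean within-man MSHQ-EjD change from baseline, with a 95% CI, in those same men for each arm.
4. As a supplementary display over all 43 and 41 followed men, show how many have antegrade ejaculation and a score no more than 0, 1, 2 or 3 points below their own baseline, counting dry men as failures. Four cut-offs avoid having to agree a single one that the documents do not supply.
5. If the paired data confirm the fall, describe the group 1 result as antegrade ejaculation retained, with a lower mean ejaculation score.

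The scores should already be in hand, since the plan collects them at all three time points. The cost is one extra table and a less favourable group 1 result.

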**-Methods of the study:**

**Pre-operative Evaluation:**

- History, which includes IPSS, the International Index of Erectile Function 5 items Questionnaire (IIEF-5Q), and the Male Sexual Health Questionnaire-Ejaculatory Dysfunction Short Form (MSHQ-EjD).

- Physical examination, which includes a digital rectal examination.

- A pre-operative lab study, which includes urine analysis, hemoglobin, creatinine, and PSA levels.

-Trans abdominal ultrasonography to determine prostate volume and post void residual (PVR) urine volume.

- Uro-flow-metry (Qmax).

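### Table 10's semen rows are headed n=43 vs 41, but the semen-volume results reproduce only among men who still ejaculated (35 vs 8; 34 vs 8), so neither the volume nor the sperm-concentration statement compares the randomised groups.

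*Combined protocol and SAP*

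**What the plan says.** The Follow up section lists what is measured at the two visits: "All patients will be followed-up regularly at 3 and 6 months postoperatively with the IPSS, Qmax, PVR, IIEF-5Q, MSHQ-EjD Short Form, and rates of complications". Semen analysis is not in that list. The Pre-operative Evaluation section describes "A pre-operative lab study, which includes urine analysis, hemoglobin, creatinine, and PSA levels", together with questionnaires, examination, ultrasound and uroflowmetry, and again does not mention semen.

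The Statistical analysis section assigns tests by distribution. Variables treated as normal are "compared between the two groups utilizing unpaired Student's T- test"; for the others, "Quantitative non-parametric data were presented as median and interquartile range (IQR) and were analyzed by Mann-Whitney test". It gives no method for an outcome that does not exist in some men.

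Table 10 then reports post-operative semen volume and sperm concentration at 3 and 6 months under headings n=43 and n=41. The same table gives preserved ejaculation in 35 and then 34 of 43 men in Group 1, and in 8 of 41 men in Group 2 at both visits. Two conclusions follow in the text: "Semen volume (after three and six months) was insignificantly different between both groups", and "Sperm concentration (after three and six months) was significantly lower in group 1 than group 2 (P value<0.05". Neither says that it applies only to men who ejaculated, and no separate denominator is given.

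**The concern.** A man with no antegrade ejaculate has no ordinary specimen in which to measure volume or concentration. If the semen rows cover only men who ejaculated, the table sets about 80% of Group 1 against about 20% of Group 2. The operation itself decides who belongs to each subset, so randomisation no longer balances them. The eight Group 2 men may have differed from the Group 1 men before surgery, and no reported baseline lets a reader check.

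At stake are two statements that will be read as comparisons of randomised arms. One is a statistically significant deficit in sperm concentration with the new technique. The other is an absence of difference in semen volume. A reader who trusts the column headings takes each to rest on 84 men.

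**Working it through.** **Inputs, all from Table 10.**
- Semen volume, 3 months: 2.37 (SD 0.78) vs 2.01 (SD 0.58) mL; difference 0.362, P 0.223, upper limit 0.953. The lower limit is printed as -229, read here as -0.229.
- Semen volume, 6 months: 2.41 (SD 0.78) vs 2.49 (SD 0.73) mL; difference -0.079, P 0.797, limits -0.165 and 0.535.
- Men with preserved ejaculation: 35 vs 8, then 34 vs 8.

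**Step 1: which denominator gives the printed volume results?** The test is the planned unpaired t-test with pooled variance:

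s² = [(n₁−1)s₁² + (n₂−1)s₂²] / (n₁+n₂−2); SE = s·√(1/n₁ + 1/n₂); CI = difference ± t₀.₉₇₅·SE.

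For 3 months at 35 vs 8: s = √[(34·0.78² + 7·0.58²)/41] = 0.750; SE = 0.750·√(1/35 + 1/8) = 0.294; t = 0.362/0.294 = 1.23 on 41 df.

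| Visit | n assumed | P | 95% CI | Printed |
|---|---|---|---|---|
| 3 months | 35 vs 8 | 0.225 | -0.231 to 0.955 | P 0.223; -0.229 to 0.953 |
| 3 months | 43 vs 41 | 0.018 | 0.063 to 0.661 | no match |
| 6 months | 34 vs 8 | 0.796 | -0.692 to 0.534 | P 0.797; upper limit 0.535 |
| 6 months | 43 vs 41 | 0.633 | -0.407 to 0.249 | no match |

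The counts of men with preserved ejaculation reproduce the printed results within rounding; the column headings do not. The printed 6-month lower limit of -0.165 fits neither denominator.

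**Step 2: sperm concentration.** Only medians and quartiles are printed: 35 (13.75–82) vs 72 (62.75–89.25) at 3 months, and 32.5 (13–72) vs 86 (76–106.75) at 6 months. The Mann-Whitney P can therefore only be approximated, here by interpolating a distribution through the quartiles (an assumed shape). At 35 vs 8 and 34 vs 8 this gives about 0.06 and 0.001; at 43 vs 41, about 0.0005 and 0.00000001. The printed values are 0.036 and 0.005. They lie much closer to the counts of ejaculating men, but this is not an exact match.

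**Step 3: how selected are the subsets?** Preserved ejaculation at 3 months is 35/43 = 81.4% vs 8/41 = 19.5%, a ratio of 4.17. At 6 months it is 34/43 = 79.1% vs 19.5%, a ratio of 4.05. Table 11 shows that men who ejaculated also differ by age: 70.83% preserved under 60 years, 52.17% at 60–70 and 14.29% over 70 (3 months).

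**Step 4: can the data still give a direction for sperm concentration?** Assume that Group 1 surgery never removes ejaculation that Group 2 surgery would leave. Men who would ejaculate after either operation are then 19.5/81.4 = 24% of the Group 1 men who ejaculated at 3 months (25% at 6 months), about 8 men. With the interpolated distributions, their Group 1 median could lie anywhere from about 7 to 108 at 3 months (Group 2: 72) and from about 6 to 93 at 6 months (Group 2: 86). Both ranges include the Group 2 median.

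**Step 5: the same check on Table 4.** Post-operative MSHQ-EjD is also headed 43 vs 41.
- 3 months, 10.26 (1.42) vs 9.63 (1.77), difference 0.632: P is 0.284 at 35 vs 8 (printed 0.284) and 0.074 at 43 vs 41.
- 6 months, 10.62 (1.76) vs 10.38 (2.26), difference 0.243: P is 0.741 at 34 vs 8 (printed 0.741) and 0.583 at 43 vs 41.

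The scheduled ejaculatory score carries the same unlabelled restriction.

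**The case against.** Several objections have force and limit the point.

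- **Nothing is concealed about ejaculation itself.** The first rows of Table 10 give the preservation rates, and the text reports that difference before turning to semen. This stands: the fault is an unlabelled denominator, not a hidden result.
- **The text does not claim causation.** It says that concentration was lower in one group than in the other. That is so, but an unqualified significance statement between randomised arms invites a causal reading. A reader might equally infer from this review that the sperm-concentration difference has been shown not to be a treatment effect. The documents do not support that either: the bounds in step 4 are wide in both directions.
- **Absence from a list is not proof of absence.** A reader might infer that no pre-operative semen value was ever taken, or that semen analysis was added after the fact. White cell count is in neither list, yet Table 5 reports it before and after surgery. The lists show only that semen measures were not listed, and the results show only that no baseline was reported.
- **The concentration n is inferred.** This stands; only volume reproduces.
- **Counting men without preserved ejaculation as 0 mL.** It is tempting to say that this overturns the volume result, since the means become 2.37·35/43 = 1.93 vs 2.01·8/41 = 0.39 mL at 3 months. Yet giving every ejaculating man in both groups the same 2.4 mL already produces a difference of 2.4·(0.814 − 0.195) = 1.49 mL, against 1.54. The analysis mostly restates the preservation rate. The documents also do not define preserved ejaculation, so 0 mL for the other men is an assumption.

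**Conclusion.** The point holds in this form. The 43 vs 41 heading is wrong for semen volume, which was analysed in 35 vs 8 and 34 vs 8 men; this rests on the printed means, SDs and P values and a pooled t-test. Sperm concentration very probably rests on the same men, because it needs a specimen, but that needs confirming from the data. The subsets form after randomisation, differ about fourfold in size relative to their arms, and have no reported baseline. Neither semen statement can therefore be read as a comparison of the randomised groups. The effect on semen is unidentified; it has not been shown to be absent. The post-operative MSHQ-EjD rows in Table 4 share the denominator error, which matters more for the trial's aims because that score is a scheduled outcome.

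**What to change.** 1. In Table 10, print the actual n for each semen row from the data (35 vs 8 and 34 vs 8 for volume).
2. Label these rows as restricted to men who ejaculated, exploratory, and not listed in the Pre-operative Evaluation or Follow up sections.
3. Report sperm concentration descriptively, without P values, and delete the sentence stating that it was significantly lower in Group 1.
4. Limit the semen-volume sentence to men who ejaculated, and refer the reader to the preserved-ejaculation rows for the comparison of all followed men.
5. Report pre-operative semen values if they exist; otherwise state that they were not collected.
6. Check the 6-month volume lower limit, printed as -0.165 (34 vs 8 gives -0.69).
7. Correct the denominators of the post-operative MSHQ-EjD rows in Table 4 in the same way.

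A 0 mL analysis over all 43 vs 41 men is at most an optional sensitivity analysis, with its assumption stated.

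The cost is relabelling and rewording on data already held. The price is the loss of one statistically significant result, reported at two visits.

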**Table 11: Relation between age groups and preservation of ejaculation**

	<60 years (n=24)	(60-70) years (n=46)	>70 years (n=14)	P value
After 3 months	17 (70.83%)	24 (52.17%)	2 (14.29%)	0.003*
After 6 months	17 (70.83%)	23 (50%)	2 (14.29%)	0.004*

\*Significantly different as P value  $\leq 0.05$

Preserved ejaculation after three and six months were significantly higher in patients <60 years than (60-70) and >70 years (P value  $< 0.05$ ).

**Figure 20:** Preserved ejaculation after 3 months of the studied groups.

**Figure 21:** Preserved ejaculation after 6 months of the studied groups.

[figure not shown]
**Table 12: Relation between size of prostate groups and (preservation of ejaculation and rate of complications)**

		$\leq 60$ ml (n=51)	$>60$ ml (n=33)	P value	RR (95% CI)
Preserved ejaculation	After 3 months	25 (49.02%)	18 (54.55%)	0.621	0.9(0.59:1.37)
	After 6 months	25 (49.02%)	17 (51.52%)	0.823	0.95(0.62:1.47)
		(n=57)	(n=33)		
Intraoperative	Capsular perforation	1 (1.75%)	2 (6.06%)	0.034*	---
	Intraperitoneal bladder perforation	0 (0%)	1 (3.03%)		
	Blood transfusion	0 (0%)	3 (9.09%)		
Early postoperative	Severe irritative LUTs	5 (8.77%)	6 (18.18%)	0.488	---
	Clot retention	3 (5.26%)	3 (9.09%)		
	Stress incontinence	2 (3.51%)	1 (3.03%)		
Late postoperative	Stricture bulbar urethra	0 (0%)	3 (9.09%)	0.309	---
	Bladder neck contracture	3 (5.26%)	0 (0%)		

[figure not shown]
\*Significantly different as P value  $\leq 0.05$ , CI: Confidence interval, RR: Relative risk

Preserved ejaculation, early and late postoperative complications were insignificantly different between both groups.

[figure not shown]
Intraoperative complications were significantly lower in patients with prostate volume  $\leq 60$  ml than  $>60$  ml (P value=0.034).

**Figure 22:** Preserved ejaculation after 3 months of the studied groups.

**Figure 23:** Preserved ejaculation after 6 months of the studied groups.

[figure not shown]
**Figure 24:** Complications of the studied groups.

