**Table 5: Laboratory investigation of the studied groups**

[figure not shown]
		Group 1 (n=45)	Group 2 (n=45)	P value	Mean difference (95% CI)
Hemoglobin (g/dL)	Preoperative	13.34±1.85	13.88±1.35	0.121	-0.535(-1.21: 0.145)
	Postoperative	12.29±1.73	12.55±1.58	0.466	-0.256(-949: 0.438)
WBC (10^9/L)	Preoperative	8.23±3.27	8.1±2.88	0.842	0.13(-1.161: 1.42)
	Postoperative	10.18±2.09	10.55±3.22	0.524	-0.366(-1.50:0.772)
Creatinine (mg/dL)	Preoperative	1.18±0.41	1.07±0.36	0.195	0.106(-0.055: 0.267)
	Postoperative	1.11±0.24	1.1±0.33	0.874	0.009(-0.112: 0.132)
Total PSA (ng/mL)	Median	2.13	4.2	0.001*	1.41(0.60: 2.30)
	IQR	1.39 - 3.8	2.6 - 5.3		

\*Significantly different as P value  $\leq 0.05$ , WBC: White blood cell, CI: Confidence interval, PSA: Prostate-specific antigen

[figure not shown]
Hemoglobin, WBC and creatinine were insignificantly different at preoperative and postoperative between both groups.

Total PSA was significantly lower in group 1 than group 2 as (P value =0.001).

[figure not shown]

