**Table 7: PVR (ml) and Qmax (ml/sec) of the studied groups**

		Group 1 (n=43)	Group 2 (n=41)	P value	Mean difference (95% CI)
PVR (mL)	Preoperative	356 (250-380)	340 (289-391)	0.345	14(-20:48)
	3 months postoperative	55 (43.5-68.5)	39 (29-52)	0.003*	-13(-22: -4)
	6 months postoperative	49 (42.5-72)	34(22-47)	<0.001*	-21(-29: -12)
Qmax (mL/sec)	Preoperative	4.92±1.73	4.5±1.88	0.270	0.42(-0.334: 1.178)
	3 months postoperative	19.04±4.77	21.73±4.63	0.01*	-2.696(-4.738: -0.654)
	6 months postoperative	18.78±5.16	19.71±6.22	0.457	-0.93(-3.407: 1.55)

[figure not shown]
\*Significantly different as P value  $\leq 0.05$ , PVR: Postvoid residual, Qmax: Maximum urinary flow rate, CI: Confidence interval

PVR was insignificantly different at preoperative between both groups and was significantly higher at (3 months and 6 months) postoperative in group 1 than group 2 as (P value =0.003 and <0.001 respectively).

Qmax was significantly lower at 3 months postoperative in group 1 than group 2 as (P value =0.03) and was insignificantly different at (preoperative and 6 months postoperative) between both groups.

**Figure 12:** PVR of the studied groups.

**Figure 13:** Qmax of the studied groups.

[figure not shown]

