**Table 8: Intraoperative factors of the studied groups**

		Group 1 (n=45)	Group 2 (n=45)	P value	Mean difference or RR (95% CI)
Operative time (min)	Mean <math>\pm</math> SD	33.51 $\pm$ 11.49	40.53 $\pm$ 14.64	0.013*	-3.42(-11.15: 4.31)
	Range	15 – 60	18 – 75		
Blood transfusion		1 (2.22%)	2 (4.44%)	1	0.49(0.04:5.59)

[figure not shown]
\*Significantly different as P value  $\leq$ 0.05, CI: Confidence interval, RR: Relative risk

Operative time was significantly lower in group 1 than group 2 as (P value =0.013).

Blood transfusion was insignificantly different between both groups.

**Figure 14:** Operative time of the studied groups.

[figure not shown]
**Figure 15:** Blood transfusion of the studied groups.

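### Table 12's late-complication P of 0.309 should be about 0.03 to 0.05, Table 8's operative-time difference is Table 6's prostate-volume entry, and five rank-based differences carry the opposite sign to the rest

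*Combined protocol and SAP*

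**What the plan says.** The Statistical analysis section sets the threshold: "A two tailed P value $< 0.05$ was considered statistically significant". Categorical variables "were analyzed utilizing the Chi-square test or Fisher's exact test when appropriate". Non-normal variables are shown as median and IQR and compared by Mann-Whitney; no effect estimator is named for them.

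- **Table 12** (prostate volume up to 60 mL vs above 60 mL) gives late events as stricture 0 vs 3 and bladder neck contracture 3 vs 0, with P = 0.309. The complication percentages use 57 and 33 patients; the ejaculation rows use 51 and 33. The text concludes: "Preserved ejaculation, early and late postoperative complications were insignificantly different between both groups".
- **Table 9** heads its late block with 43 and 41 patients and prints P = 0.699.
- **Table 8** gives operative time as 33.51 ± 11.49 vs 40.53 ± 14.64 min, P = 0.013. After a leading minus sign, the difference cell reads "3.42(-11.15: 4.31". Table 6 prints the same string for prostate volume.
- **Tables 5 and 7** head their last column as a mean difference, although PSA and PVR are shown as medians. PSA (2.13 vs 4.2) carries "1.41(0.60: 2.30". Postoperative PVR (55 vs 39; 49 vs 34) carries -13 and -21, while the text says PVR was "significantly higher at (3 months and 6 months) postoperative in group 1 than group 2".
- **Table 10** uses one mixed heading (median difference, mean difference or RR). Sperm concentration (35 vs 72; 32.5 vs 86) carries +37 and +54.

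No table states the direction of subtraction.

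**The concern.** A row in which one complication occurs only in large prostates and the other only in smaller ones should not give P = 0.309 in a table of 90 patients. If the value is wrong, a result below the report's own threshold is described as non-significant. The summary sentence also passes over a complete separation of late complication types by volume.

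In Table 8 the printed interval includes zero beside P = 0.013, so the interval and the P value cannot both describe the same comparison.

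In Tables 5, 7 and 10, anyone who extracts differences from the tables, for a meta-analysis for example, would take the wrong sign for PVR, PSA and sperm concentration, and could not say what kind of difference was estimated.

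**Working it through.** **1. Which test Table 12 used.** Treat each complication block as a 2 × (k+1) table with a no-event column, and apply the Pearson chi-square on 57/33.

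| Block | Counts (≤60 mL; >60 mL), last = none | Chi-square (df) | P | Printed |
|---|---|---|---|---|
| Intraoperative | 1, 0, 0, 56; 2, 1, 3, 27 | 8.68 (3) | 0.0338 | 0.034 |
| Early | 5, 3, 2, 47; 6, 3, 1, 23 | 2.43 (3) | 0.4889 | 0.488 |
| Late | 0, 3, 54; 3, 0, 30 | 6.95 (2) | 0.0309 | **0.309** |

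The method recovers the first two printed values (the second by truncation) but not the third. The first two rows assume one event per patient. The late row needs no such assumption, because each volume group has only one type of late event. The same method also gives Table 9's intraoperative P (0.6204, printed 0.620) and early P (0.5063, printed 0.506, with the contracture line left out).

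**2. The late row in full.** Expected counts for each complication are 3 × 57/90 = 1.9 and 3 × 33/90 = 1.1; for no event they are 53.2 and 30.8.

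Chi-square = 1.9²/1.9 + 1.9²/1.1 + 1.1²/1.9 + 1.1²/1.1 + 0.8²/53.2 + 0.8²/30.8 = 1.900 + 3.282 + 0.637 + 1.100 + 0.012 + 0.021 = 6.95.

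With 2 df, P = exp(-6.95/2) = 0.031. On 51/33 the statistic is 6.60 and P = 0.0369.

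**3. Exact test.** Four of six expected counts are below 2, so the exact test named in the Statistical analysis section applies. For a strictures and b contractures in the smaller-volume group of size n out of N, the table probability is C(3,a) C(3,b) C(N-6, n-a-b) / C(N, n). Sum the tables no more probable than the one observed:

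- 57/33: observed 0.01282 and its mirror image 0.01282, plus (0,1) and (1,0) at 0.01086 each, plus (0,0) at 0.00178: P = 0.0491.
- 51/33: 0.01398 × 2 + 0.00272: P = 0.0307.

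**4. Type or rate.** Any late event is 3 vs 3 patients. On 57/33, chi-square P = 0.48 and Fisher P = 0.67; on 51/33, 0.58 and 0.68. None of these is 0.309 either. Stricture alone gives Fisher 0.046 (57/33) or 0.057 (51/33); contracture alone gives 0.30 or 0.28.

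**5. Table 9's late denominator.** Counts of 1 and 1 vs 2 and 2 give P = 0.6997 on 45/45 and 0.662 on the printed 43/41. The printed 0.699 matches the first by truncation and does not match the second.

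**6. Table 8, operative time** (n = 45 per group).

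- Difference = 33.51 - 40.53 = -7.02.
- Pooled SD = √[(11.49² + 14.64²)/2] = 13.16; SE = 13.16 × √(2/45) = 2.774.
- 95% CI = -7.02 ± 1.987 × 2.774 = -12.53 to -1.51; t = -2.53, P = 0.013, as printed.
- The printed half-width, (4.31 + 11.15)/2 = 7.73, would need a pooled SD of 18.45. That is impossible with SDs of 11.49 and 14.64, but plausible for prostate volume, where Table 6 shows an SD of 17.71.

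**7. Signs and estimators.** Qmax at 3 months is 19.04 - 21.73 = -2.69, which agrees with the printed entry (minus sign, then "2.696(-4.738: -0.654"), so this row is Group 1 minus Group 2.

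| Row | Group 1 minus Group 2 medians | Printed |
|---|---|---|
| PVR preoperative | 356 - 340 = +16 | +14 |
| PVR 3 months | 55 - 39 = +16 | -13 |
| PVR 6 months | 49 - 34 = +15 | -21 |
| PSA | 2.13 - 4.2 = -2.07 | +1.41 |
| Sperm 3 months | 35 - 72 = -37 | +37 |
| Sperm 6 months | 32.5 - 86 = -53.5 | +54 |

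Five of the six rows have the opposite sign. In size, the sperm entries match differences of medians (the second after rounding); the PVR and PSA entries do not.

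**The case against.** The strongest reply concerns Table 12. Its title speaks of the rate of complications, and on rate the sentence is right: three late events on each side. Only the comparison of types crosses 0.05, on six events, with an exact P of 0.049 on the printed denominator. This stands and limits how the corrected result may be worded. It does not rescue 0.309, which no version of the rate comparison produces. The counts are also visible in the table, so nothing is concealed from a careful reader.

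The volume split is not described in the Methods or Statistical analysis sections, and the inclusion criteria limit prostate volume to 20–60 mL. The column above 60 mL therefore holds patients outside the stated range. That is fair, and it is a further reason to treat the result as descriptive.

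A dropped zero (0.0309 printed as 0.309) is the likely explanation, but an inference. So is the 45/45 denominator in Table 9. Only the raw output can settle either.

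On the rank-based rows, the columns do carry labels; the labels fit poorly rather than being absent. A single estimator such as a Hodges-Lehmann shift could have produced all the entries, since it need not equal the difference of medians. The text also gives the correct direction for PVR, PSA and sperm concentration, so a reader of the prose is not misled. What remains is inconsistent signs within the columns and no named estimator.

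**Conclusion.** The point holds.

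- **Table 12:** 0.309 is not the P value of its row. By the table's own method it is 0.031; by the exact test it is 0.049 (57/33) or 0.031 (51/33). All are below the stated threshold, so calling the late row non-significant is wrong as a statement about type and right only as a statement about overall rate. With six events, no multiplicity adjustment and an unplanned split, the finding is descriptive.
- **Late denominators:** they are inconsistent between and within Tables 9 and 12, and the exact P depends on the choice.
- **Table 8:** the printed effect is about half the true one (3.42/7.02 = 0.49), and its interval contradicts the P value. The conclusion on operative time is unchanged.
- **Tables 5, 7 and 10:** five rank-based entries appear to have reversed signs. The direction of the preoperative PVR row and the estimator used cannot be settled from the document.

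Confidence is high for the arithmetic in Tables 12 and 8. The cause of the 0.309 and the estimator behind the rank-based rows remain inferences.

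**What to change.** 1. **Late complications.** Check the raw output. State one denominator for late events in Tables 9 and 12, either those followed (43/41 and 51/33) or all randomised (45/45 and 57/33), and recompute both late P values on it. In Table 12 print the exact P: 0.031 on 51/33 or 0.049 on 57/33. Use the exact test for the other two blocks too; on 57/33, if each event is a different patient, it gives about 0.009 (intraoperative) and 0.42 (early), with conclusions unchanged.
2. **Wording under Table 12.** Replace the late-complication statement with, for example: late complication types differed by prostate volume (strictures only above 60 mL, contractures only at 60 mL or below), while the overall late rate did not differ (three events in each group); this rests on six events in an unplanned comparison without multiplicity adjustment. Note beside it that the inclusion criteria give an upper volume limit of 60 mL.
3. **Table 8.** Print -7.02 (-12.53: -1.51). Keep the P value and the sentence.
4. **Tables 5, 7 and 10.** Confirm the direction and estimator of every rank-based row, including preoperative PVR. Report all differences as Group 1 minus Group 2 and name the estimator in a footnote (for example a Hodges-Lehmann shift). Do not label the PVR and PSA rows as mean differences or as differences of medians.

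The cost is a recheck of existing output, a few table cells, a footnote and one reworded sentence. No new data are needed.
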